### **6.1.2. AEs of clinical interest**

#### **Cardiac arrhythmia**

Cardiac arrhythmia will be determined based on Cardiac arrhythmias (SMQ, broad and narrow) and Ventricular tachyarrhythmias (SMQ, narrow).

#### **Cardiac failure**

Cardiac failure will be determined based on Cardiac failure SMQ (narrow).

#### **Interstitial Lung Disease**

Interstitial Lung Disease (ILD) will be determined based on Interstitial lung disease (SMQ, narrow). All treatment emergent ILD events will be summarized by preferred terms.

#### **Leukostasis**

Leukostasis will be obtained for preferred term of “leukostasis syndrome”.

## **Hypertension**

Hypertension will be determined based on Hypertension (SMQ, narrow).

## **Hepatic Disorders**

Hepatic disorders will be obtained from the SOC of “Hepatobiliary Disorders”.

## **Cytopenic Adverse Events**

Cytopenic adverse events will be obtained from preferred terms of “neutropenia”, “neutrophil count decreased” “febrile neutropenia”, “thrombocytopenia” “ platelet count decreased” and “anaemia”.

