## **6.2. Overdose**

Any dose of study drug administered in excess of that specified in this protocol is considered to be an overdose. Signs and symptoms of an overdose that meet any Serious Adverse Event criterion must be reported as a Serious Adverse Event in the appropriate time frame and documented as clinical sequelae to an overdose.

There is no specific experience in the management of ibrutinib overdose in patients. No maximum tolerated dose was reached in the Phase 1 study in which subjects received up to 12.5 mg/kg/day (1,400 mg/day). Healthy subjects were exposed up to single dose of 1,680 mg. One healthy subject experienced reversible Grade 4 hepatic enzyme increases (AST and ALT) after a dose of 1,680 mg. Subjects who ingested more than the recommended dosage should be closely monitored and given appropriate supportive treatment. Refer to Section 12 for further information regarding AE reporting (refer to Section 12.3.2 for Special Reporting Situations).

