### **9.4.2. Clinical Laboratory Tests**

Blood samples for serum chemistry and hematology will be collected. The investigator must review the laboratory results, document this review, and record any clinically relevant changes occurring during the study in the adverse event section of the CRF. The laboratory reports must be filed with the source documents.

The following tests will be performed. See [TIME AND EVENTS SCHEDULE](#) for exact time points of these and other assessments.

- Hematology Panel (local laboratory)
  - hemoglobin
  - hematocrit
  - absolute neutrophil count
  - platelet count
  - total white blood cell (WBC) count
  - absolute lymphocyte count
- Serum Chemistry Panel (local laboratory)
  - albumin
  - ALT
  - calcium
  - creatinine
  - lactic acid dehydrogenase (LDH)
  - alkaline phosphatase
  - AST
  - blood urea nitrogen (BUN)
  - glucose
  - potassium

-phosphate	-total bilirubin
-sodium	-uric acid
-total protein	
• Coagulation (central laboratory)	
-PT/INR	-activated partial thromboplastin time
• Serum immunoglobulin (central laboratory)	
-IgG	-IgA
-IgM	
• $\beta$ 2 -microglobulin (central laboratory)	

Samples will be collected at Screening.

- Serum Viscosity (local laboratory)

Serum viscosity at Screening is optional. After Screening, it should be performed at the discretion of the treating physician in any subject with signs and symptoms suggesting a hyperviscosity syndrome.

- Hepatitis B Screening (local laboratory)
  - HBsAg
  - Hepatitis B core antibody

If HBsAg is positive, the subject will be excluded. Hepatitis B DNA needs to be performed if Hepatitis B core antibody is positive. DNA PCR needs to be confirmed negative prior to first dose of administration in subjects who are Hepatitis B core Ab positive. During study treatment and for at least 12 months following the last dose of treatment, regular monitoring of Hepatitis B PCR and liver enzymes and prophylactic antiviral medication should be considered per published guidelines.

- Hepatitis C Screening (local laboratory)
  - Hepatitis C antibody

If Hepatitis C antibody is positive, RNA PCR needs to be performed and confirmed negative prior to first dose administration. Patient with History of Hepatitis C virus infection should have documented 24 weeks of sustained virologic response (SVR) in order to be eligible for the study.

- Pregnancy Test (local laboratory)

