## **12.1. Definitions**

### **12.1.1. Adverse Event Definitions and Classifications**

#### **Adverse Event**

An adverse event is any untoward medical occurrence in a clinical study subject administered a medicinal (investigational or non-investigational) product. An adverse event does not necessarily have a causal relationship with the intervention. An adverse event can therefore be any unfavorable and unintended sign (including an abnormal finding), symptom, or disease temporally associated with the use of a medicinal (investigational or non-investigational) product, whether or not related to that medicinal (investigational or non-investigational) product. (Definition per International Conference on Harmonisation [ICH])

This includes any occurrence that is new in onset or aggravated in severity or frequency from the baseline condition, or abnormal results of diagnostic procedures, including laboratory test abnormalities.

Note: The sponsor collects adverse events starting with the signing of the ICF (refer to Section 12.3.1, All Adverse Events, for time of last adverse event recording).

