### 6.1. Adverse Events

The verbatim terms used in the CRF by investigators to identify adverse events will be coded using the Medical Dictionary for Regulatory Activities (MedDRA). Treatment-emergent adverse events (TEAEs) are those adverse events occurring after the first dose of study drugs and within 30 days following the last dose of study drug or initiation of subsequent antineoplastic treatment, whichever occurs earlier; any adverse event that is considered study drug-related regardless of the start date of the event; or any adverse event that is present at baseline but worsens after the first administration of study drug in severity or is subsequently considered drug-related by the investigator. If the event occurs on the day of the initial administration of study agent, and either event time or time of administration are missing, then the event will be assumed to be treatment emergent. If the event date is recorded as partial or completely missing, then the event will be considered to be treatment emergent unless it is known to be prior to the first administration of study agent based on partial onset date or resolution date. All reported treatment-emergent adverse events will be included in the analysis. For each adverse event, the number and percentage of subjects who experience at least 1 occurrence of the given event will be summarized.

Summary tables will be provided for treatment-emergent adverse events:

- Overall summary of all TEAEs
- TEAEs by System Organ Class (SOC), preferred term (PT) and toxicity grade 3 or higher
- TEAE with frequency of at least 10% by SOC, PT and toxicity grade 3 or higher
- Drug-related TEAEs by SOC, PT and toxicity grade 3 or higher
- Serious TEAEs by SOC, PT and toxicity grade 3 or higher
- TEAEs leading to dose modification (including dose interruption and dose reduction) by SOC, PT and toxicity grade 3 or higher
- TEAEs leading to discontinuation of study drug by SOC, PT and toxicity grade 3 or higher
- TEAEs leading to death by SOC and PT
- TEAEs by SOC, PT and toxicity by period
- TEAE of interest for COVID-19 infection by PT and toxicity grade
- Serious TEAE of interest for COVID-19 infection by PT and toxicity grade

- TEAE of interest for COVID-19 infection leading to death by PT

In addition to the summary tables, listings will be provided as appropriate.

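### The cytopenia term list pairs a count-decreased term with the diagnosis for neutrophils and platelets but not for haemoglobin, so red-cell events may be under-counted in that one grouped table.

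*SAP*

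**What the plan says.** SAP 6.1.2 defines the adverse events of clinical interest. The cytopenic group is a closed list: "Cytopenic adverse events will be obtained from preferred terms of" six named terms, which are "neutropenia”, “neutrophil count decreased” “febrile neutropenia”, “thrombocytopenia” “ platelet count decreased” and “anaemia". No standardized query and no catch-all wording is attached. For the liver group the SAP says "Hepatic disorders will be obtained from the SOC of “Hepatobiliary Disorders"; it names no individual terms and no query. The amendment history shows that both groups were added in SAP version 2.

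Three other places determine what reaches these groups:

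- Protocol 12.1.1 extends the adverse event definition to "or abnormal results of diagnostic procedures, including laboratory test abnormalities".
- Protocol 9.4.2 tells the investigator to "record any clinically relevant changes occurring during the study in the adverse event section of the CRF".
- SAP 6.1 gives the coding route: "The verbatim terms used in the CRF by investigators to identify adverse events will be coded using the Medical Dictionary for Regulatory Activities (MedDRA".

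**The concern.** By listing 'neutrophil count decreased' beside 'neutropenia' and 'platelet count decreased' beside 'thrombocytopenia', the SAP accepts that one clinical event can be recorded either as a diagnosis or as a laboratory finding. It covers both forms for two cell lines and only the diagnosis for the third, and gives no reason.

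Elsewhere the three lines are treated alike. The baseline cytopenia definition in SAP 4.1 uses a laboratory threshold for each of haemoglobin, platelets and neutrophils, and protocol 1.1.2.3.2 names neutropenia, thrombocytopenia and anemia together.

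At stake is whether the grouped count reflects what happened to subjects or how the event was worded. A related question arises for the liver group, because the SAP does not say whether enzyme or bilirubin increases reported as adverse events count as hepatic disorders.

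**Working it through.** The plan states no figure on this point, so there is none to reproduce. The check compares the texts and then works out the scale.

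**1. The six terms by cell line (SAP 6.1.2)**

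| Cell line | Diagnosis terms | Count-decreased term |
|---|---|---|
| Neutrophils | neutropenia, febrile neutropenia | neutrophil count decreased |
| Platelets | thrombocytopenia | platelet count decreased |
| Red cells | anaemia | none |

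**2. Two parallel events followed through the rules**

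- *Platelets.* A clinically relevant fall is entered on the adverse event page (protocol 9.4.2) in laboratory wording and coded to 'platelet count decreased' (SAP 6.1). The term is listed, so the subject is counted.
- *Haemoglobin.* A clinically relevant fall is entered in the same way and coded to a haemoglobin-decreased term. The term is not listed, so the subject is not counted unless another listed term is present.

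The second path assumes that the dictionary keeps a haemoglobin-decreased term separate from 'anaemia'. The documents do not say so, although the neutrophil and platelet pairs in the list show that kind of separation.

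**3. Is the omission a stated choice?** For major hemorrhage, SAP 6.1.1 says explicitly that laboratory terms are excluded from the query. The cytopenia and hepatic definitions contain no such statement.

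**4. Scale**

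Input: about 17 subjects (SAP 1.2), all assumed treated.

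- Maximum effect of one missed subject on the group incidence: 1/17 = 5.9 percentage points.
- Effect on the overall group if that subject also has any other listed term: 0.
- If results are shown only by preferred term, the 'anaemia' row does not change. What is missing is a separate haemoglobin row.

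The documents give no event rate. As an assumption only, let q be the share of subjects whose sole cytopenic event is coded to an unlisted haemoglobin term, independently across subjects. Then the expected number missed is 17q, and the chance of missing at least one is 1 − (1 − q)^17.

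| Assumed q | Expected missed | Chance of at least one |
|---|---|---|
| 5% | 17 × 0.05 = 0.85 | 1 − 0.95^17 = 58% |
| 10% | 17 × 0.10 = 1.7 | 1 − 0.90^17 = 83% |
| 20% | 17 × 0.20 = 3.4 | 1 − 0.80^17 = 98% |

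These rows show sensitivity to q; they do not estimate it.

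**5. Hepatic group.** The SAP names one system organ class. Whether enzyme and bilirubin increases fall inside it depends on the dictionary, and neither document describes that. This part can only be put as a check to make.

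**The case against.** The strongest reply is that nothing is lost from the report. SAP 6.1 tabulates all TEAEs by system organ class and preferred term, so a haemoglobin or enzyme event appears there under its own name. SAP 6.2 adds descriptive statistics, CTCAE-graded summaries, shift tables and a listing of liver function abnormalities, all from measured values and so independent of wording. Protocol 12.3.1 also asks for a diagnosis where possible, and 'anaemia' is listed.

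Most of this stands, and it limits the consequence to the grouped table. It does not correct that table. Adding preferred-term rows by hand can count a subject with both terms twice. The preference for a diagnosis concerns signs and symptoms with a common cause, and does not ensure that an isolated haemoglobin fall is written as anaemia. If it did, the two count terms already listed would be unnecessary.

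A reader might go further in four ways that the documents do not support:

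- *That anaemia and hepatic events are under-counted as a matter of fact.* This depends on future wording and coding, so only 'may be' is justified.
- *That the liver group certainly misses enzyme rises.* This needs knowledge of the dictionary that the documents do not supply. The enzyme increase in protocol 6.2 does not help: it concerns one healthy subject after a 1,680 mg dose, not the study population at 420 mg.
- *That the haemoglobin treatment criterion in protocol 4.1 raises the stakes.* It governs entry, not event counting. Anaemia already present at baseline generally becomes treatment-emergent only if it worsens or is judged drug-related.
- *That 5.9 points measures the bias.* It is the most that one missed subject can contribute.

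It is also fair to say that choosing a system organ class, a query or a term list is within the SAP's discretion. The objection here is to unequal treatment within one list.

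**Conclusion.** The point holds in a limited form. As written, the cytopenia list can omit a red-cell event while counting the equivalent neutrophil or platelet event, so red-cell events may be under-counted in the grouped table of adverse events of clinical interest. The size is unknown, with the per-subject ceiling shown above. It rests on some investigators recording a haemoglobin fall as a laboratory finding and on that wording being coded to a term other than 'anaemia'.

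The hepatic part is conditional on enzyme- and bilirubin-increase terms being coded outside the named system organ class, which has to be checked.

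The affected summaries are descriptive. The primary endpoint, alpha, power, full TEAE tables and laboratory outputs do not change. Severity is the lowest.

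**What to change.** - Add 'haemoglobin decreased' to the cytopenia list in SAP 6.1.2.
- For hepatic disorders, check the MedDRA version in use. If enzyme- and bilirubin-increase terms lie outside the named system organ class, add them by name or use a standardized query, as the SAP already does for arrhythmia, interstitial lung disease and hypertension.
- If laboratory-type terms are meant to be left to SAP 6.2, say so and apply the same rule to all three cell lines.

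The cost is a few terms in the SAP search list and one dictionary check, with no new data collection. It should be done before the analysis, so that the choice of terms cannot appear to follow the results.

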## **Infections**

Infections will be obtained from the SOC of “Infections and Infestations”.

## **Tumor Lysis syndrome**

Tumor Lysis syndrome will be obtained from preferred term of “tumor lysis syndrome”.

## **Ischemic stroke**

Ischemic central nervous system vascular conditions (SMQ).

## **Hypersensitivity**

This definition will be specified in DPS, separatory.

## **Rash**

All preferred terms containing the word “Rash”.

## **6.2. Clinical Laboratory Tests**

All clinical laboratory tests will be displayed for the subjects included in the safety analysis set. Laboratory data for hematology and serum chemistry tests will be reported in SI units. Applicable laboratory results will be graded according to NCI-CTCAE Version 4.03.

The following laboratory tests will be analyzed:

- Hematology: hemoglobin, platelet count, white blood cell (WBC) count, absolute neutrophil count (ANC), absolute lymphocyte count, and hematocrit
- Chemistry: calcium, sodium, potassium, glucose, total bilirubin, blood urea nitrogen (BUN), creatinine, total protein, aspartate aminotransferase (AST), alanine aminotransferase (ALT), alkaline phosphatase, phosphate, lactic acid dehydrogenase (LDH), uric acid and albumin.
- serum immunoglobulin levels (IgG, IgM, IgA)

- coagulation

Descriptive statistics and change from baseline will be presented for all laboratory tests with continues values at scheduled time points.

For categorical variables, frequency tabulations of the changes from baseline results will be presented in pre versus postintervention cross-tabulations (with classes for Low, Normal, and High). Frequency tabulations of the abnormalities will be made. A listing of subjects with laboratory results will be provided. A listing of subjects with liver function abnormality will also be provided. Parameters with predefined NCI-CTCAE toxicity grades will be summarized. Change from baseline to the worst adverse event grade experienced by the subject during the study will be provided as shift tables.

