**TIME AND EVENTS SCHEDULE**

	Screening Phase	Treatment Phase							Post-Treatment/ Follow-Up Phase	
		1	5-16 q4 weeks	17	21	25+ q8 weeks	Suspected PD Visit	End-of-Treatment Visit a	Post-treatment Pre-disease Progression Phase q12 weeks	Post-disease Progression Phase q12 weeks
Study Weeks		1	5-16 q4 weeks	17	21	25+ q8 weeks	Suspected PD Visit	End-of-Treatment Visit a	Post-treatment Pre-disease Progression Phase q12 weeks	Post-disease Progression Phase q12 weeks
Study Day of the Study Week		1	1	1	1	1				
Study Windows	-30 days		± 3 days		± 3 days	± 3 days	Anytime	± 7 days	± 7 days	± 7 days
Study Drug Administration										
ibrutinib 420 mg PO		Continuous dosing until PD or unacceptable toxicity								
Dispense Study Drug (ibrutinib)		X	X	X	X	X				
Administrative Procedures										
Informed consent b	X									
Confirm eligibility	X	X								
Medical history and Demographics	X									
Safety Assessments										
Physical exam (height at Screening only)	X c	X c	X d	X d	X d	X d	X c	X c	X c	
Eye-related symptom assessment	X	X	X	X	X	X	X	X	X	
ECOG status	X	X		X	X	X	X	X	X	
Vital signs	X	X	X p	X	X	X	X	X	X	
ECG	X	Additional assessments may be performed if clinically indicated during the course of the study.								

	Screening Phase	Treatment Phase							Post-Treatment/ Follow-Up Phase	
		1	5-16 q4 weeks	17	21	25+ q8 weeks	Suspected PD Visit	End-of-Treatment Visit a	Post-treatment Pre-disease Progression Phase q12 weeks	Post-disease Progression Phase q12 weeks
Study Weeks		1	5-16 q4 weeks	17	21	25+ q8 weeks	Suspected PD Visit	End-of-Treatment Visit a	Post-treatment Pre-disease Progression Phase q12 weeks	Post-disease Progression Phase q12 weeks
Study Day of the Study Week		1	1	1	1	1				
Study Windows	-30 days		± 3 days		± 3 days	± 3 days	Anytime	± 7 days	± 7 days	± 7 days
Clinical Laboratory Assessments										
Hematology	X	X n	X	X	X	X	X	X	X	
Serum chemistry	X	X n	X	X	X	X	X	X		
Coagulation (PT, INR, and aPTT)	X			X				X		
Pregnancy test e	X									
Hepatitis serologies	X o									
Serum viscosity (optional) f	X									
β2-microglobulin	X									
Efficacy Assessments										
Serum immunofixation g	X									
Serum protein electrophoresis (SPEP)	X	X	X	X	X	X	X	X	X	

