## **9. STUDY EVALUATIONS**

### **9.1. Study Procedures**

#### **9.1.1. Overview**

The study is divided into a Screening Phase, a Treatment Phase, and a Follow-up Phase. The **TIME AND EVENTS SCHEDULE** summarizes the frequency and timing of efficacy, PK, and safety measurements applicable to this study. All subjects enrolled will undergo the same study procedures throughout the study unless otherwise noted.

The total blood volume to be collected estimated is approximately 30 mL for the Screening Phase, 72 mL from Week 1 to Week 24, 12 mL every 8 weeks from Week 25, 15 mL at the suspected PD visit, 15 mL at the End-of-Treatment (EOT) Visit, and 7 mL every 12 weeks for the Post-treatment Pre-disease Progression Phase. Repeat or unscheduled samples may be taken

for safety reasons or for technical issues with the samples. The volume of blood to be drawn is considered to be normal and acceptable for subjects participating in a cancer clinical study and is deemed reasonable over the time frame of the study.

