##### **9.1.4.1. Post-treatment Pre-disease Progression Phase**

Subjects who discontinue the treatment for reasons other than PD will be followed every 12 weeks ( $\pm 7$  days) by clinic visit until disease progression is confirmed, regardless of initiation of subsequent anticancer treatment. Procedures performed during this period are outlined in [TIME AND EVENTS SCHEDULE](#).

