##### **9.1.4.2. Post-disease Progression Phase**

After investigator confirmed disease progression, subjects will be contacted to assess survival status, the use of alternative antineoplastic therapy and occurrence of any other malignancy approximately every 12 weeks ( $\pm 7$  days) by clinic visit or telephone until death, withdrawal by subject, lost to follow-up, or study terminated by Sponsor, whichever comes first. At the time of the primary analysis and at study closure, a survival sweep will be conducted. All subjects who are on study and not known to have died prior to the survival sweep will be contacted at that time.

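### The laboratory worst-grade window has no end at treatment stop, so haematology grades arising under a later anticancer therapy can enter the ibrutinib shift tables

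*SAP*

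**What the plan says.** SAP 6.2 grades applicable laboratory results by NCI-CTCAE v4.03 and then specifies: "Change from baseline to the worst adverse event grade experienced by the subject during the study will be provided as shift tables". Protocol 11.5 (Clinical Laboratory Tests) uses the same sentence. The population is every treated subject: "All clinical laboratory tests will be displayed for the subjects included in the safety analysis set". Neither section gives an on-treatment window, and SAP 2.1 says only that visits follow the CRF record.

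The Time and Events Schedule marks haematology in the column headed "Post-treatment Pre-disease Progression Phase q12 weeks". Serum chemistry has no mark there; its last is at the End-of-Treatment visit. Protocol 9.1.1 budgets blood for the same phase: "7 mL every 12 weeks for the Post-treatment Pre-disease Progression Phase". Protocol 9.1.4.1 says who enters it, "Subjects who discontinue the treatment for reasons other than PD will be followed every 12 weeks", and for how long: "until disease progression is confirmed, regardless of initiation of subsequent anticancer treatment".

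Adverse events are handled differently. SAP 6.1 counts events after first dose and "within 30 days following the last dose of study drug or initiation of subsequent antineoplastic treatment, whichever occurs earlier". It also keeps any event judged related to study drug, whatever its start date, and any baseline event that worsens after first dose or is later judged drug-related.

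**The concern.** Protocol 9.1.1 divides the study into screening, treatment and follow-up, so a window covering the whole study includes the post-treatment visits. A neutrophil, platelet or haemoglobin grade recorded under the next therapy, possibly long after the last ibrutinib dose, then qualifies as the subject's worst grade in a table meant to describe ibrutinib. Protocol 1 (Existing Therapies in WM) says the disease is most often treated in China with rituximab alone or with chemotherapy, and it mentions the toxicities of chemotherapy. A low count under a later regimen is therefore plausible.

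At stake is attribution in the safety description. There is no control arm, and Protocol 1.2 says the data are to support full approval in China. SAP 6.1.2 names cytopenic adverse events as events of clinical interest. A late low count could appear as Grade 4 in the laboratory table and be absent from the TEAE tables, with no stated rule to explain the difference.

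**Working it through.** The point rests on no stated figure except the planned number of subjects. That number is sound: with n = 17, the exact two-sided 90% lower limit is 0.311 at 9 responders and 0.364 at 10, so success needs at least 10. The exact one-sided error at 32% is 0.0204 and the power at 69.8% is 0.892, which meets the stated 85%. Nothing below alters this.

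**Step 1: is the laboratory window open?** SAP 6.2 and Protocol 11.5 both run it over the study, and no other section of either document narrows it. The phrase about the worst adverse event grade does not bring in the TEAE window. It follows a sentence on laboratory parameters with predefined CTCAE grades, and its only time qualifier is the study.

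**Step 2: are there graded values after treatment?** In the Time and Events Schedule the haematology row has nine marks, the ninth under the post-treatment, pre-progression column. Serum chemistry has eight and ends at the End-of-Treatment visit. Among the scheduled safety panels the issue therefore concerns haematology.

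**Step 3: can those values fall under a new therapy?** Yes. Protocol 9.1.4.1 continues the visits until confirmed progression whether or not another therapy has begun.

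**Step 4: who can be affected?** Each of these conditions must hold:
- the subject stopped ibrutinib for a reason other than progression;
- a new therapy started before progression;
- the grade under that therapy is worse than any grade on ibrutinib;
- it is present at a 12-weekly draw or in an unscheduled sample that is recorded.

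Subjects who have progressed are not exposed through scheduled sampling, because in that phase "subjects will be contacted to assess survival status, the use of alternative antineoplastic therapy and occurrence of any other malignancy" and no laboratory tests are scheduled.

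**Step 5: size.** Change in a rate = k/17, where k is the number of subjects whose worst grade in a given parameter arises only under later therapy.

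| k | Change in rate (percentage points) |
|---|---|
| 0 | 0 |
| 1 | 1/17 = 5.9 |
| 2 | 2/17 = 11.8 |
| 3 | 3/17 = 17.6 |

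The documents give no value for k. The range 0 to 3 is an assumption, and the top row requires all three subjects to change category in the same parameter.

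**The case against.** A reader might infer that cytopenias from the next therapy are in fact counted against ibrutinib. The documents show only that they can be. All the conditions in step 4 must be met, and Protocol 9.2 works against one of them by asking that subsequent therapy be withheld, where possible, until progression is confirmed. Sampling every 12 weeks can also miss a short cytopenia. This part of the objection stands.

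A reader might also infer that the window is what would make laboratory and TEAE rates disagree. It is at most one cause. Protocol 9.4.2 has the investigator record clinically relevant laboratory changes as adverse events, while the shift tables grade results directly, so the two can differ even with identical windows. Nor is the TEAE window a plain cut-off, since drug-related events count regardless of date.

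Other protections exist. Cytopenic adverse events are defined by preferred term in SAP 6.1.2, and an unrelated event with onset under later therapy falls outside the TEAE definition. SAP 6.2 provides a listing of laboratory results, and SAP 4.5 summarises subsequent antineoplastic therapy. A careful reader could trace a late value, although the shift table itself would stay as programmed. Finally, the error can only raise apparent toxicity, in a table with no test or threshold attached. That limits its importance but does not make the attribution right.

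**Conclusion.** The point holds in a limited form. Followed literally, SAP 6.2 allows haematology grades that arise under a later anticancer therapy to enter the ibrutinib worst-grade shift tables, and neither document closes that window. The number of affected subjects is unknown and may be zero; each would move a rate by 5.9 percentage points on 17 treated subjects. The effect is limited to descriptive haematology tables. The documents do not support extending it to ORR, the sample size, the power or the TEAE tables, none of which uses this window. The reading of the text is firm; the size depends on how many subjects stop without progression and start new therapy, which the plan does not state. The correction is still worth making, because the rule is explicit, a single subject is visible at this sample size, and the cost is trivial.

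**What to change.** In SAP 6.2, state that worst-grade shifts and abnormality frequencies use values from first dose to the earlier of 30 days after last dose or the start of subsequent antineoplastic therapy. State also that later values are listed separately, with the start date of any subsequent therapy beside them. The listing matters because SAP 6.1 keeps drug-related events whatever their date, so a late count linked to such an event must remain visible.

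The cost is one SAP sentence and one on-treatment flag in the laboratory dataset. No new data are needed, and the follow-up visits do not change. Protocol 11 leaves specific details to the SAP, and Protocol 17.1 requires a formal amendment for any change to the protocol, so the matching sentence in Protocol 11.5 need be aligned only if the protocol is amended for other reasons. The small downside is that a late-onset cytopenia outside the window would appear only in the listing.
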